3.1.3 Clinical Trials

Human experience with CFI-400945 consists of a dose-finding phase I study (CFI-400945-CL-001) in which subjects with treatment refractory advanced solid tumours were evaluated. As of December 20, 2017, interim safety data are available for a total of 50 subjects treated in 10 cohorts dosed over the range of 3 – 96 mg/day in 28-day continuous cycles. A RP2D of 64 mg/day for the continuous dosing schedule has been established. DLTs in the 72 mg and 96 mg cohorts included G3 neutropenia in both cohorts, G4 febrile neutropenia in the 64 mg and 96 mg cohorts, and asymptomatic G4 lipase elevation in the 72 mg cohort. The common related AEs ($\geq 10\%$) were fatigue, nausea, decreased appetite, diarrhea, neutrophil count decreased and neutropenia. Two possibly related AEs led to study discontinuation; serum amylase/lipase increase (72 mg/day) and febrile neutropenia (64 mg/day). Dose-limiting toxicity (DLT) occurred in four subjects; these were serum amylase/lipase increase and neutropenia (72 mg/day), and two cases of febrile neutropenia (64 mg/day and 96 mg/day). To add an additional safety margin to mitigate risk of early onset myelosuppression seen in a minority of patients, more intensive hematologic monitoring was added to this period, and a 14 day run in (Cycle 0), consisting of 7 days of CFI-400945 dosing followed by 7 days without CFI-400945 dosing was implemented. No cardiac toxicity was observed in the phase I dose escalation or expansion. Please refer to the most recent version of the Investigator Brochure for full details.

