5.0 PATIENT EVALUATION FLOWSHEET: PRE-TREATMENT, ON STUDY, AND AFTER TREATMENT

All patients entered on study must be evaluated according to the schedule outlined below with documentation submitted according to the schedule in Appendix IV.

Required Investigations	Pre-study (≤ 7 days prior to enrollment)	Biweekly cycles 1 and 2 and then Weekly	Day 1 each cycle, and as clinically indicated	Every 8 weeks	4 weeks after end of last cycle date	3 monthly follow-up (only required for pts without PD and ongoing toxicities ¹) then every 6 months until death
History and Physical Exam*						
Including: height ² and weight, ECOG performance status, documentation of all measurable and non-measurable disease, clinical tumour measurements (if applicable); Vital signs: blood pressure, heart rate, temperature	X		X		X	
Laboratory Procedures/Assessments*						
CBC (neutrophils, platelets)	X	X ³			X ⁴	X ⁴
PTT, PT/INR	X					
Serum creatinine ⁵ , calcium, magnesium, phosphate, bilirubin, ALP, AST, ALT, LDH, albumin, glucose, amylase/lipase ⁶	X		X		X ⁴	X ⁴
TSH ⁷	X		X		X ⁴	X ⁴
Pregnancy Test ⁸	X		X ⁹			
Urinalysis	X ¹⁰					
Radiology						
Tumour Imaging (Chest/upper abdomen CT scan; bone scan ¹¹ ; other scans as necessary to document disease) ¹²	X ¹³ (within 21 days prior to enrollment or 28 days if negative)			X	X ¹⁴	X ¹⁴
Other Investigations						
EKG	X					
LVEF	X ¹⁰					
Archival Tumour Tissue	X ¹⁵					
Correlative Studies Blood Sampling	X ¹⁶	See Section 12.0 for details				
Tumour biopsies	X ¹⁷	X ¹⁷				
Patient Drug Administration Diary (CFI-400945)		Each cycle				
Adverse events	X	Continuously			X ¹	

Footnotes on next page ...

- * Pre-treatment blood draws and physical exams may be done up to two working days prior to treatment if necessary (e.g. Friday for treatment on Monday, or to accommodate holidays). In order to ensure that nadir counts are not missed, every effort should be made to do interim blood draws within 24 hours of the day specified in the protocol. If a patient shows an AST or ALT $\geq 3 \times$ ULN together with total bilirubin $\geq 2 \times$ ULN, refer to Appendix II for further instructions on cases of increases in liver biochemistry and evaluation of Hy's Law. These cases should be reported as SAEs if, after evaluation, they meet the criteria for a Hy's law case or if any of the individual liver test parameters fulfill any of the SAE criteria

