- 1 Adverse events felt to be related to protocol therapy will be followed until resolved to \leq Grade 2. Reversible durvalumab- related adverse events \geq grade 3 should be followed until resolved to baseline grade including related toxicity that occurs in the follow up period. Irreversible events may not need to be followed. Contact CCTG to discuss. Adverse Events to be evaluated using the NCI Common Terminology Criteria for Adverse Events (CTCAE v5.0) (see Appendix V).
- 2 Height is only required at baseline.
- 3 Hematology is to be done twice weekly cycles 1 and 2. Provided patient has not experienced grade 3 or 4 neutropenia, hematology can be done weekly cycle 3 onward. For patients on for 6+ cycles, contact CCTG for a waiver if appropriate. See section 7 for additional monitoring of patients with toxicity.
- 4 Required at 4 weeks. To be done additionally every 3 months thereafter to follow abnormal lab results felt related until resolved to \leq Grade 2.
- 5 If creatinine $> 1.5 \times$ ULN, calculated CrCl is required and must meet eligibility criteria for re-treatment. For patients who have discontinued CFI-400945 and are continuing on durvalumab alone, criteria for creatinine clearance may be lower. Please contact CCTG to discuss.
- 6 Required at baseline then as clinically indicated. It is preferable that both amylase and lipase parameters are assessed. For sites where only 1 of these parameters is routinely measured then either lipase or amylase is acceptable.
- 7 Free T3 and free T4 will be measured if TSH is abnormal.
- 8 For women of childbearing potential only (urine or serum test). Within 72 hours prior to enrollment. Pregnancy test (in women of childbearing potential), as part of Pre-Study Evaluation, may include an ultrasound to rule-out pregnancy.
- 9 As clinically indicated in WOCBP.
- 10 Required at baseline then as clinically indicated.
- 11 Bone scan is required at baseline for all patients. Thereafter, bone scan is only required to be repeated if positive at baseline to confirm CR/iCR, PR/iPR or SD/iSD, and/or when PD is suspected and as clinically indicated.
- 12 To ensure comparability, baseline scans and subsequent scans to assess response must be performed using identical technique (i.e. scans performed immediately following bolus contrast administration using a standard volume of contrast, the identical contrast agent, and preferably the same scanner). Maintain schedule every 8 weeks, even if cycles are delayed.

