7.1.1 Drug Administration

Cycle	Agent(s)	Dose	Route	Duration	Schedule	Cycle duration (days)
1	CFI-400945	32 mg	Oral	-	Days 1-7 then Days 15-21	28
2 onwards				-	Daily*	28
2 onwards	Durvalumab	1500 mg	IV	60 min	Day 1	28

* *An intermittent schedule may be used (see 7.1.3).*

Cycle 1 will consist of CFI-400945 administered at the starting dose on a one week on and one week off schedule.

Depending on the toxicity observed in Cycle 1, Cycle 2 Day 1 will begin with durvalumab administration and CFI-400945 at either 32 mg continuously or on an intermittent schedule (Section 7.1.3 Table 1) continuously in subsequent 28-day repeating treatment cycles. Patients who experience no myelosuppression in 2 consecutive cycles may have CFI-400945 dose escalated to 40 mg (see 7.1.3). Patients may have the CFI-400945 dose reduced at any time due to toxicity. If either agent is held for toxicity, the other agent should also be held unless the toxicity is neutropenia alone.

Patients will take CFI-400945 by mouth at least 1 hour before, and 2 hours after, any food and should be encouraged to take the CFI-400945 at the same time each day at the time they find most convenient and are least likely to forget. On days when both CFI-400945 and durvalumab are administered, the timing of durvalumab administration in relation to CFI-400945 is not important, as long as they are started on the same day.

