7.1.3 Dose Levels

The following are dose levels for CFI-400945, which will be titrated according to the degree of toxicity:

DL+1 (escalation)	DL1	DL-1	DL-2
40 mg daily	32 mg daily	32 mg / 5 days per week (5 days on/2 days off)	32 mg / 3 days per week
Note: intermediate dose levels/schedules may be selected after review of data by CCTG and investigators.			

Durvalumab will be administered as a flat dose of 1500 mg for patients > 30 kg in weight. If patient weight falls to ≤ 30 kg, weight-based dosing at 20 mg/kg will be administered. No dose reductions are planned.

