7.1.5 Dose Modifications – CFI-400945

Doses will be reduced for hematologic and other adverse events. Dose adjustments are to be made according to the system showing the greatest degree of toxicity. Adverse events will be graded using the NCI Common Terminology Criteria for Adverse Events (CTCAE) (see Appendix V).

Reported and/or expected toxicities include, but are not limited to: amylase/lipase increases, neutropenia and leucopenia, febrile neutropenia fever and chills, infection, typhlitis/diarrhea, fatigue, increased liver function tests, nausea, vomiting, mucositis. The guidelines which follow outline dose adjustments for several of these toxic effects. If a patient experiences several adverse events and there are conflicting recommendations, please use the recommended dose adjustment that reduces the dose to the lowest level. Doses should only be modified for toxicity related to CFI-400945.

Diarrhea > Grade 1 is not a common toxicity of CFI-400945. Patients who experience diarrhea should be carefully evaluated for possible immune mediated colitis and managed accordingly.

Following any interruption of dosing for toxicity as described below, CFI-400945 should not be restarted until ANC $\geq 1.5 \times 10^9/L$ and platelets $\geq 100 \times 10^9/L$ and resolution of all drug related toxicity to \leq grade 2.

Table 1. Guidelines for CFI-400945 Dose Modifications for Neutropenia:

ANC (for dosing during cycle AND worst in prior cycle)	Cycles	Dose and management ^{1,3,4}
$\geq 1.5 \times 10^9/L$	All	No change. Note: If $\geq 1.5 \times 10^9/L$ for cycles 2 and 3 (or any 2 cycles after cycle 1) despite continuous oral dosing and having received at least 90% of planned doses ² : may escalate 1 DL
$1.0 \times 10^9/L - <1.5 \times 10^9/L$	All	Hold ⁴ until $\geq 1.5 \times 10^9/L$. No change in dose for next cycle.
Inability to receive at least 75% of planned dose within prior cycle	All	Hold ⁴ until $\geq 1.5 \times 10^9/L$.
$<1.0 \times 10^9/L$ (with no fever) <5 days ⁵		Reduce 1 DL
$<1.0 \times 10^9/L \geq 5$ days or febrile neutropenia	Cycle 1	Discontinue ⁶
	Other cycles	Hold ⁴ until $\geq 1.5 \times 10^9/L$. Reduce 2 DL

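### Minor safety point: when CFI-400945 is raised to 40 mg, blood counts may stay weekly, because no rule restores twice-weekly CBC for a dose increase

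*Combined protocol and SAP*

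**What the plan says.** **Counts.** Section 5.0, footnote 3, requires CBC twice weekly in cycles 1 and 2. After that: "Provided patient has not experienced grade 3 or 4 neutropenia, hematology can be done weekly cycle 3 onward". The footnote refers to section 7 for additional monitoring, but only for patients with toxicity.

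**Escalation.** Section 7.1.1 says: "Patients who experience no myelosuppression in 2 consecutive cycles may have CFI-400945 dose escalated to 40 mg". Table 1 in 7.1.5 words the condition differently. It asks for ANC of at least 1.5 × 10⁹/L in cycles 2 and 3, "or any 2 cycles after cycle 1) despite continuous oral dosing", with at least 90% of planned doses received. Footnote 2 to Table 1 allows re-escalation after a reduction on the same conditions, if there was no febrile neutropenia and no need for growth factors.

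**Return to twice-weekly counts.** Section 7.1.5 names these triggers: grade 3 or 4 ANC (Table 1, footnote 3), grade 2 or 3 thrombocytopenia, and thrombocytopenic bleeding (Table 2). A dose increase is not among them.

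**Experience at 40 mg.** Section 3.1.4 reports 8 patients started at 40 mg/day. Two had grade 4 neutropenia, one had febrile neutropenia, five had dose holds and three had reductions for neutropenia. The starting dose was then lowered to 32 mg.

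**The concern.** Neutropenia is the toxicity that has driven dosing in this trial: 3.1.4 describes starting doses of 64, 48, 40 and now 32 mg. Two clean cycles at 32 mg show tolerance of 32 mg. They do not show tolerance of 40 mg, which is the highest dose level in the current plan.

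Growth factors may not be given prophylactically (7.2.1), so the main protection is to find a falling count and hold the drug. A short episode is more likely to be missed on weekly draws. A lasting one is found later, while daily dosing continues. Detection time also feeds a dosing rule. After cycle 1, Table 1 reduces by one dose level for afebrile ANC below 1.0 × 10⁹/L lasting under 5 days, and by two levels if it lasts 5 days or more. Counts a week apart cannot date the onset well enough to tell these apart.

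Only first detection is at stake. Once grade 3 or 4 ANC is seen, Table 1 footnote 3 already restores twice-weekly counts.

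**Working it through.** The plan gives no figure to reproduce here, so the check reads the rules side by side and then compares the two sampling schedules.

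**1. Can the first 40 mg cycle fall in the weekly period?**
- Weekly CBC is permitted from cycle 3 (5.0, footnote 3).
- Under 7.1.1 read literally, cycles 1 and 2 can be the two clean cycles, so the earliest 40 mg cycle is cycle 3.
- Under Table 1 the two cycles come after cycle 1, so the earliest is cycle 4.
- Both lie in the weekly period, and no text in 5.0 or 7.1 links count frequency to a dose increase.

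**2. Who is affected?** Patients with no grade 3 or 4 neutropenia. Those who have had it do not qualify for weekly counts under footnote 3, so most re-escalations after a neutropenia reduction are already covered.

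**3. Dose and counts per 28-day cycle.** The fair comparison is cycle 2, which is dosed daily, and not cycle 1: "Cycle 1 will consist of CFI-400945 administered at the starting dose on a one week on and one week off schedule".
- Cycle 2: 28 × 32 = 896 mg, 8 CBCs.
- Escalated cycle: 28 × 40 = 1120 mg, 4 CBCs if weekly.
- 1120/896 = 1.25, a 25% higher dose with half the counts.

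**4. Mean delay to the first draw.** Assumptions: onset at a random time, ANC stays low until found, no unscheduled CBC, twice-weekly draws 3 and 4 days apart. For gaps g, mean delay = Σg² / (2Σg).
- Weekly: 49/14 = 3.5 days, longest 7.
- Twice weekly: (9 + 16)/14 = 1.79 days, longest 4.
- Difference: 1.71 days, or about 1.7 daily doses before the hold.

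**5. Share of drops already past 5 days at the first draw.** This is Σmax(0, g − 5)/Σg, with the 5-day limit taken from Table 1.
- Weekly: (7 − 5)/7 = 29%.
- Twice weekly: 0%, since no gap exceeds 4 days.

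**6. Short episodes.** The documents give no episode lengths, so 3 to 5 days is an assumed range. The chance that an episode of D days is sampled at least once is min(1, D/7) weekly and [min(D,3) + min(D,4)]/7 twice weekly.

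| D (days) | Weekly | Twice weekly |
|---|---|---|
| 3 | 43% | 86% |
| 4 | 57% | 100% |
| 5 | 71% | 100% |

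**The case against.** The strongest objection is that no risk is shown in the patients concerned. They must have two cycles with ANC at or above 1.5 × 10⁹/L on continuous dosing with at least 90% of doses taken, or no myelosuppression in the 7.1.1 wording. The step is 25%, and nobody may escalate at all. The delay figures describe 7-day against 3- and 4-day sampling and would be the same for any patient from cycle 3 on. There are also safeguards. Dosing stops below 1.5, before the 1.0 level that triggers a reduction. Weekly counts are permitted, not required, so an investigator may draw more often. Patients are told to report significant toxicity (7.1.4). All of this stands, and it is why the point is minor. It does not supply the missing rule.

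A reader might infer more than the documents support, in four ways:

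- **That the plan's own rationale demands intensive counts at each new dose.** Section 3.1.3 speaks of measures to "mitigate risk of early onset myelosuppression seen in a minority of patients, more intensive hematologic monitoring was added to this period", but that passage describes the phase I study and its 14-day run-in. Footnote 3 in 5.0 gives no reason for the twice-weekly counts here.
- **That weekly counts breach the plan's nadir standard.** The flowsheet says "In order to ensure that nadir counts are not missed, every effort should be made to do interim blood draws within 24 hours" of the specified day. This asks sites to keep to the scheduled days and sets no frequency.
- **That counts could lapse altogether after escalation.** The text is "For patients on for 6+ cycles, contact CCTG for a waiver if appropriate". The site must ask and the coordinating group must agree, so a waiver granted just after a dose rise is speculation.
- **That the 40 mg rates apply.** Grade 4 neutropenia in 2/8 = 25% (exact 95% CI 3% to 65%) comes from unselected starters and does not transfer to patients chosen for two clean cycles.

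**Conclusion.** The gap is real and minor. For patients without grade 3 or 4 neutropenia, the first cycles at 40 mg may run on weekly CBC, and nothing in 5.0 or 7.1 restores twice-weekly counts for a dose increase.

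The size is a mean detection delay of 3.5 against 1.8 days, with 29% against 0% of persistent drops already past 5 days when first sampled. This rests on the assumptions in step 4 of the working. The 29% is the share past the limit before anyone could act, not a forecast of two-level reductions. It would be lower if an earlier draw caught ANC between 1.0 and 1.5 and stopped dosing. The event rate after escalation and the number who will escalate are not in the documents.

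The change is still worth making because it reuses a pattern the plan already has. Counts are twice weekly in cycles 1 and 2, and for two cycles after grade 2 thrombocytopenia even though the dose is unchanged. No effect on the recommended dose of 32 mg or on the primary endpoint follows from this point.

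**What to change.** Add to 5.0 footnote 3 and to Table 1 in 7.1.5: *After any escalation or re-escalation of CFI-400945, CBC is done twice weekly for the first two cycles at the higher dose; weekly CBC may then resume if there has been no grade 3 or 4 neutropenia.*

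Two cycles is a judgement, and one would also be defensible. In its favour, two of the four patients with neutropenia among the first five at 64 mg had their grade 3 or 4 event within the second cycle (3.1.4).

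The cost is 16 − 8 = 8 extra CBCs per escalated patient over two cycles. If 1 to 6 patients escalate (an assumption), that is 8 to 48 CBCs in all. The test is already in the schedule. The downsides are some extra visits, for patients who may live up to about an hour and a half's drive away (the example in 4.1.12), and some holds for brief dips that weekly counts would not have shown.

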5.1 Follow-up for Ineligible Patients

The follow-up requirements for ineligible patients who have received no protocol therapy include submission of the Baseline Report and End of Treatment Report. Data submission for ineligible participants who have received at least one dose of protocol therapy should be followed according to the protocol to allow for treatment and adverse event assessment.

6.0 ENTRY/ENROLLMENT PROCEDURES

6.1 Entry Procedures

All enrollments will be done through the CCTG web-based, password-operated Electronic Data Capture (EDC) system. Complete details regarding obtaining a password, accessing the system and enrolling patients will be provided at the time of study activation and will also be included in the “EDC Generic Data Management Guidebook”, posted on the IND.239 trial specific web-site. If sites experience difficulties accessing the system and/or enrolling patients please contact the help desk (link in EDC) or the IND.239 Study Coordinator.

All eligible patients enrolled on the study by the participating treatment centre will be assigned a serial number which must be used on all documentation and correspondence with CCTG.

The following information will be required:

- trial code (CCTG IND.239)
- patient's initials (may be coded)
- informed consent version date, date signed by patient, name of person conducting consent discussion and date signed
- tissue banking/optional consent version date
- confirmation of the requirements listed in Section 4.0, including dates of essential tests and actual laboratory values
- height and weight

6.2 Study Enrollment

Enrollment will be provided electronically.

At the time of enrollment, all data reported within the Patient Enrollment folder must be accurate, complete and verifiable against source documentation. If a system query is issued indicating that the patient is not eligible, enrollment within the EDC system will not proceed. CCTG should be contacted for assistance if needed. Under no circumstances should inaccurate data be entered in order to permit enrollment.

Note: The validity of results of the trial depends on the authenticity of and the follow-up of all patients entered into the trial. Under no circumstances, therefore, may an allocated patient’s data be withdrawn prior to final analysis, unless the participant withdraws from the trial and requests that data collection/submission cease from the point in time of withdrawal.

All eligible patients admitted to the trial will be followed by the coordinating centre. It is the responsibility of the physician in charge to satisfy himself or herself that the patient is indeed eligible before requesting enrollment.

All patients are to be followed until death or until sites are informed by CCTG that further follow-up is no longer required. The follow-up requirements for ineligible patients are outlined in Section 5.1.

6.3 Inclusion of Women and Minorities

This trial will only enroll women. Men are excluded because the historical comparison cohort used to benchmark the response rate from this study included only one male patient. There are no exclusions based on race or ethnicity in this trial. This study, however, will be presented to patients through the major cancer-treatment institutions of the Canadian provinces, to which all racial/ethnic groups have equal access. The intention, therefore, is to recruit subjects from racial/ethnic groups in close approximation to the incidence of the disease in these groups.

7.0 TREATMENT PLAN

Although the Canadian Cancer Trials Group acts as the coordinating agency for the trial, the responsibility for treatment of patients rests with the individual investigator.

In accordance with CCTG policy, protocol treatment is to begin within 2 working days of patient enrollment.

7.1 Treatment Plan

No pharmacokinetic or pharmacodynamic interaction is expected to occur and given the non-overlapping toxicity profiles, no formal dose escalation phase will occur. A safety review after the enrollment of 6 patients, who received at least 1 cycle and up to 3 cycles, will be conducted prior to reopening to further accrual. If needed, the starting dose of CFI-400945 will be reduced by one dose level.

7.1.1 Drug Administration

Cycle	Agent(s)	Dose	Route	Duration	Schedule	Cycle duration (days)
1	CFI-400945	32 mg	Oral	-	Days 1-7 then Days 15-21	28
2 onwards				-	Daily*	28
2 onwards	Durvalumab	1500 mg	IV	60 min	Day 1	28

* *An intermittent schedule may be used (see 7.1.3).*

Cycle 1 will consist of CFI-400945 administered at the starting dose on a one week on and one week off schedule.

Depending on the toxicity observed in Cycle 1, Cycle 2 Day 1 will begin with durvalumab administration and CFI-400945 at either 32 mg continuously or on an intermittent schedule (Section 7.1.3 Table 1) continuously in subsequent 28-day repeating treatment cycles. Patients who experience no myelosuppression in 2 consecutive cycles may have CFI-400945 dose escalated to 40 mg (see 7.1.3). Patients may have the CFI-400945 dose reduced at any time due to toxicity. If either agent is held for toxicity, the other agent should also be held unless the toxicity is neutropenia alone.

Patients will take CFI-400945 by mouth at least 1 hour before, and 2 hours after, any food and should be encouraged to take the CFI-400945 at the same time each day at the time they find most convenient and are least likely to forget. On days when both CFI-400945 and durvalumab are administered, the timing of durvalumab administration in relation to CFI-400945 is not important, as long as they are started on the same day.

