1. Hold if ANC $< 1.5 \times 10^9/L$; do not restart or start next cycle until ANC $\geq 1.5 \times 10^9/L$. 2. May also re-escalate after a prior dose reduction providing no febrile neutropenia and growth factors were not required and same conditions are met. 3. If Grade 3 or 4 ANC, CBC monitoring is required twice weekly for at least one full cycle after last event. 4. From Cycle 3 onward, CCTG may be contacted for an exemption to continue dosing if ANC $\geq 1.2 \times 10^9/L$. If cannot restart dosing within 21 days, discontinue. 5. If grade 3 neutropenia occurs in Cycle 3 onwards, contact CCTG to discuss option of no DL reduction. 6. Consult CCTG for clarification for borderline values in asymptomatic patients.		

Table 2. Guidelines for CFI-400945 Dose Modifications for Other Toxicity

Worst Toxicity	Management/Action	Dose of CFI-400945 when re-started*
Hematologic		
Grade 1 or 2 thrombocytopenia	No action. If grade 2, increase surveillance with twice weekly CBC for 2 cycles provided no further dose modification needed	No change
Grade 3 thrombocytopenia	Hold until $\geq 100 \times 10^9/L$	Reduce by 1 DL AND increase surveillance with twice weekly CBC for at least 2 cycles
Thrombocytopenic bleeding	Hold and treat, increase surveillance with twice weekly CBC	Reduce by 2 DL or discontinue, AND increase surveillance with twice weekly CBC for at least 2 cycles
Non-Hematologic**		
Grade 2 AST and/or ALT AND Grade 2 bilirubin	Discontinue	Discontinue
Hy's Law (AST or ALT $\geq 3 \times$ ULN AND total bilirubin $\geq 2 \times$ ULN)	Discontinue	Discontinue
Diarrhea Grade 2	Hold until immune mediated diarrhea excluded (or treated) and until recovered to \leq grade 1	Restart without dose reduction
Other Grade 3	Hold until \leq grade 2	Reduce by 1 DL
Other Grade 4	Discontinue	Discontinue
* If CFI-400945 cannot be restarted within 21 days, discontinue permanently.		
** Despite adequate supportive care.		

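### Sections 7.1.1 and 7.1.5 (Table 1) set different conditions for escalating CFI-400945 to 40 mg, and nothing says which governs

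*Combined protocol and SAP*

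**What the plan says.** Section 7.1.1 gives the escalation rule in one sentence: "Patients who experience no myelosuppression in 2 consecutive cycles may have CFI-400945 dose escalated to 40 mg". It then refers the reader to 7.1.3, which defines 40 mg daily as DL+1 but contains no criterion for moving to it.

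The same section describes the first cycle: "Cycle 1 will consist of CFI-400945 administered at the starting dose on a one week on and one week off schedule". Its dosing table starts durvalumab in Cycle 2.

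Section 7.1.5, Table 1, gives a second rule in its top ANC row (1.5 x 10^9/L or above). Escalation by one dose level is allowed if that ANC holds in Cycles 2 and 3 ("or any 2 cycles after cycle 1) despite continuous oral dosing and having received at least 90% of planned doses"). Footnote 2 adds a rule for patients whose dose was reduced earlier: "May also re-escalate after a prior dose reduction providing no febrile neutropenia and growth factors were not required and same conditions are met".

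**The concern.** The two rules govern the same decision, and a site can find either one first. The pointer in 7.1.1 does not lead to Table 1. It may be a stale reference, because the preceding sentence in 7.1.1 also cites a table under the wrong section number: "or on an intermittent schedule (Section 7.1.3 Table 1) continuously in subsequent 28-day repeating treatment cycles". Table 1 is in 7.1.5. That is an inference; 7.1.3 is also a valid place to look up what 40 mg daily means.

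The tie-break in 7.1.5 ("please use the recommended dose adjustment that reduces the dose to the lowest level") does not settle the matter. It applies when one patient has several adverse events with conflicting recommendations, not when two sections disagree on escalation.

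What is at stake is tolerability and uniform dosing across sites. Section 3.1.4 reports that the starting dose was lowered from 64 to 48 to 40 and then to 32 mg/day. Of the eight patients who started at 40 mg, two had grade 4 neutropenia and one had febrile neutropenia. The looser reading of 7.1.1 therefore allows a return to 40 mg with less prior exposure. It could also put a patient on 40 mg in Cycle 3, within the span of up to three cycles that the six-patient safety review covers (7.1 and 13.3). Table 1 could not.

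**Working it through.** The plan gives no figure to reproduce, so the check compares the two texts and then counts doses.

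**Inputs**
- Cycle 1: 32 mg on Days 1-7 and 15-21, which is 14 dosing days, with no durvalumab (7.1.1).
- Cycle 2 onwards: 32 mg daily for 28 days, with durvalumab on Day 1 (7.1.1).
- DL+1: 40 mg daily (7.1.3).
- Thresholds of 90% for escalation and 75% for the low-intake row (7.1.5, Table 1).

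**Step 1. The two rules side by side**

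| Condition | 7.1.1 | 7.1.5 Table 1 |
|---|---|---|
| Blood count | No myelosuppression (undefined; may include platelets) | ANC at or above 1.5 x 10^9/L |
| Cycles that count | Two consecutive; silent on Cycle 1 | Any two, Cycle 1 excluded |
| Continuous dosing | Not stated | Required |
| Doses taken | Not stated | 90% or more of planned |
| After an earlier reduction | Not stated | No febrile neutropenia, no growth factors needed, same conditions |

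Table 1 is stricter on most rows. Section 7.1.1 is stricter on consecutive cycles and, if platelets are meant, on blood counts.

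**Step 2. If Cycle 1 counts under 7.1.1 (no dosing delays)**
- Earliest 40 mg under 7.1.1: Day 1 + 2 x 28 = Day 57, the start of Cycle 3.
- Earliest 40 mg under Table 1: Day 1 + 3 x 28 = Day 85, the start of Cycle 4.
- Planned dose before 40 mg under 7.1.1: 14 x 32 + 28 x 32 = 448 + 896 = 1344 mg, with 28 continuous-dosing days and 1 durvalumab dose.
- Planned dose before 40 mg under Table 1: 448 + 896 + 896 = 2240 mg, with 56 continuous-dosing days and 2 durvalumab doses.
- Table 1 minimum if 90% applies per cycle: 0.9 x 28 = 25.2, so 26 doses per cycle and 52 in total; 448 + 52 x 32 = 2112 mg.
- Table 1 minimum if 90% is pooled: 0.9 x 56 = 50.4, so 51 doses; 448 + 51 x 32 = 2080 mg.

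**Step 3. If Cycle 1 does not count under 7.1.1**

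Both rules then give Day 85 for a patient with clean Cycles 2 and 3 and full intake. The 90% condition still separates them. The next row of Table 1 that responds to low intake is "Inability to receive at least 75% of planned dose within prior cycle", and 0.75 x 28 = 21 doses.
- Per cycle: 21 to 25 of 28 doses taken (75.0% to 89.3%), or 3 to 7 missed.
- Pooled: 42 to 50 of 56 doses taken (75.0% to 89.3%), or 6 to 14 missed with at most 7 in either cycle.

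A patient in this band with no myelosuppression meets 7.1.1, fails Table 1 and does not trigger the 75% row. Applied per cycle, a hold of 3 to 7 days for grade 2 diarrhea produces this case, since Table 2 of 7.1.5 says "Restart without dose reduction".

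**Step 4. A second case on the same reading**

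Take a patient raised to 40 mg, reduced to 32 mg with growth factors needed, who then has two clean cycles. Section 7.1.1 allows 40 mg again; footnote 2 does not.

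**Step 5. Size of the dose step, and context**
- From 28 x 32 = 896 mg to 28 x 40 = 1120 mg per cycle: 1120/896 - 1 = +25%.
- At a 40 mg/day starting dose, 5 of 8 patients needed a hold related to neutropenia (3.1.4): 63%, exact (Clopper-Pearson) 95% interval 24% to 91%. These patients started at 40 mg, so this does not measure the risk after two clean cycles at 32 mg.

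**The case against.** The strongest reply is that 7.1.1 is an overview and Table 1 the operative rule. A site setting a dose by ANC has to open Table 1, and the row it opens holds the escalation conditions. The 7.1.1 sentence also follows directly on the Cycle 2 text, so its two cycles most naturally mean continuous-dosing cycles, which removes the Day 57 against Day 85 gap. Escalation is optional under both texts, and a site can satisfy both at once. Blood counts continue and dosing is held below an ANC of 1.5 x 10^9/L whichever rule led to the escalation, apart from exemptions that CCTG may grant.

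Much of this stands. The reading that excludes Cycle 1 is plausible, the monitoring limits the harm, and the documents do not show how often the remaining cases would occur. But no text makes Table 1 govern, and the conflict survives the favourable reading, as Steps 3 and 4 show.

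It can also be said that footnote 2 is irrelevant, because a patient below 32 mg daily who goes up one level does not reach 40 mg. That does not cover a patient reduced from 40 to 32 mg daily.

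A fair point about the remedy is that simply deferring to Table 1 would drop the consecutive-cycle requirement and any platelet requirement that 7.1.1 now carries. The fix has to deal with that.

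**Conclusion.** The inconsistency is real and should be fixed. Following 7.1.1 as written can put a patient on a dose that Table 1 bars. The difference is 28 days and one full continuous-dosing cycle (896 mg planned) if Cycle 1 counts. If it does not, it is a band of 3 to 7 missed doses per cycle (6 to 14 over two cycles if pooled), plus re-escalation after a reduction.

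Confidence is high that the texts differ. The Day 57 figure depends on counting Cycle 1 and on no delays. The missed-dose band takes planned doses to be 28 per continuous cycle. Neither the number of patients affected nor the toxicity of 40 mg in patients escalated after clean cycles can be worked out from the documents. The primary endpoint, sample size and error rates are not affected.

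**What to change.** Replace the escalation sentence in 7.1.1, including its pointer to 7.1.3, with: *CFI-400945 may be escalated to 40 mg only if the escalation conditions in Section 7.1.5 Table 1 and its footnotes are met; Cycle 1 does not count.*

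Then settle three points in Table 1 so that the edit loses no safeguard:
- If consecutive cycles were meant, say so in the escalation condition.
- If platelets were meant, add a platelet count of at least 100 x 10^9/L, the restart threshold already used in 7.1.5.
- State whether the 90% applies to each cycle or to the two cycles pooled.

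The cost is one sentence and a few words, with no extra patients or procedures. Some patients would reach 40 mg 28 days later than a literal 7.1.1 allows. Patients who took less than 90% of planned doses would wait for two qualifying cycles, with some loss of dose intensity.
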